### **8.6 Premature termination of the study**

In addition to safeguarding the safety of the patients in the study, the DSMB will check for early proof of efficacy during an interim-analysis for benefit which will be performed halfway the study. If the DSMB suspects harm there will be a meeting between the DSMB, the study group and an independent statistician. During this meeting there should be a discussion about any potential causal relation between early start of postoperative oral nutrition and harm.

## **9. STATISTICAL ANALYSIS**

All analyses will be done according to the intention-to-treat approach in which all randomized patients are included, regardless of adherence to study protocol. Occurrences of the primary and secondary endpoints are compared between the treatment groups. Results are presented as risk ratios with corresponding 95% confidence intervals. A two-tailed  $P < 0.05$  is considered statistically significant. To compare the groups the data will be tested for normal distribution and an unpaired T-test will be performed when appropriate, otherwise the Mann-Whitney U or Chi-square tests.

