### **4.5 Sample size calculation**

Patients will be recruited at the outpatient clinic of the Catharina Hospital Eindhoven. Reduction of anastomotic leakage and postoperative ileus are primary outcome parameters for the sample size calculation. Anastomotic leakage is the most detrimental complication

following colorectal surgery associated with high hospital costs and also with effects on long-term general and cancer-specific outcome. We have performed two clinical studies in colorectal surgery patients that can be used as basis for the power calculation. In one study in which we compared very early enteral nutrition with very early parenteral nutrition, we observed a reduction of anastomotic leakage from 12.9% in the parenteral group to 1.6% in the enteral group. However, this effect may be confounded by the potential detrimental effect of parenteral nutrition. Early postoperative ileus reduced in this study from 35% in the parenteral group to 16% in the enterally fed patients.

In a second study, the effect of sham-feeding via chewing gum on postoperative ileus was compared with controls. In this study postoperative ileus was reduced from 47% in the controls to 27% in the intervention group. The effect on anastomotic leakage was also apparent and leak-rates reduced from 13% in the placebo group to 3% in the intervention group

Based on these previous results a power calculation can be performed. For postoperative ileus a sample size of at least 91 patients per group is needed based on a power of 0.8 and an alpha of 0.05. For anastomotic leakage a reduction of anastomotic leakage of at least 75% was observed in the previous clinical studies. Using a power of 0.8 and a drop-out percentage of 5% a total of 140 patients are needed per group. Since perioperative nutrition is a new concept, an interim analysis is performed after inclusion of 40 patients in which feasibility and safety of preoperative nutrition are assessed. All analyses will be done according to the intention-to-treat approach in which all randomised patients are included, regardless of adherence to study protocol. Occurrences of the primary and secondary endpoints are compared between the treatment groups. Results are presented as risk ratios with corresponding 95% confidence intervals. A two-tailed  $P < 0.05$  is considered statistically significant.

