## 6. METHODS

### 6.1 Primary endpoint

- Postoperative ileus

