### 6.2 Secondary endpoints

- Anastomotic leakage
- Aspiration pneumonia
- Gastric volumes preoperatively
- Length of functional recovery
- The local and systemic inflammatory response
- Surgical complications
- Length of stay
- Intestinal barrier function and local inflammation in the gut
- Need for additional surgical, radiological or endoscopic interventions
- Need for ICU admission and total length of ICU stay
- Quality of life (EQ-5D-5L and EORTC-QLQ-C30 at baseline, after 3 and 6 months)
- Cost-effectiveness ratios (iMCQ and iPCQ at baseline, after 3 and 6 months)
- Composition of faecal microbiome

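### Sections 4.5 and 9 put one P<0.05 significance rule on the primary and every secondary endpoint, with no testing order, gatekeeping, adjustment or supportive label

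*Combined protocol and SAP*

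**What the plan says.** Section 9 states "Occurrences of the primary and secondary endpoints are compared between the treatment groups" and, shortly after, "A two-tailed $P < 0.05$ is considered statistically significant". Section 4.5 contains the same two statements. The criterion names no endpoint, so it covers all of them. Section 9 adds t, Mann-Whitney or chi-square tests as the data require, so continuous secondary endpoints are tested too.

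Section 6.1 names one primary endpoint, "Postoperative ileus". Section 6.2 lists 13 secondary items, and some hold more than one comparison: "Need for ICU admission and total length of ICU stay" holds two, and "Quality of life (EQ-5D-5L and EORTC-QLQ-C30 at baseline, after 3 and 6 months" holds at least four (two questionnaires at two follow-up times).

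No section gives a testing order, an alpha allocation, a multiplicity adjustment, a condition that the primary result be positive, or a statement that secondary results are exploratory or supportive. The one ranking is the primary/secondary label, and the documents disagree on where it falls. Section 4.5 says "Reduction of anastomotic leakage and postoperative ileus are primary outcome parameters for the sample size calculation", and sections 2.1 and 12.1(d) also treat both outcomes as primary. Section 6.1 names ileus alone, and section 6.2 lists leakage as secondary.

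**The concern.** If ileus shows no difference, the plan still allows a lone P below 0.05 on, for example, "Length of stay", "Length of functional recovery" or one questionnaire at one visit to be declared statistically significant. With a dozen or so such tests, at least one chance finding is far more likely than 1 in 20. The plan gives a reader no means of telling a confirmatory result from a supportive one. What is at stake is how secondary findings may be described, above all after a null primary result.

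**Working it through.** **1. The plan's own figures.** The documents state no familywise error rate. The nearest check is whether the sample size reserves any alpha for other tests. For ileus, section 4.5 gives 47% against 27%, alpha 0.05, power 0.8 and 91 per group. With pooled variance and a two-sided test:

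n = [1.960 × √(2 × 0.37 × 0.63) + 0.842 × √(0.47 × 0.53 + 0.27 × 0.73)]² / 0.20² = (1.338 + 0.562)² / 0.04 = 90.3, so 91.

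This matches. For leakage, 13% against 3% with a continuity correction gives 134 per group, and 134 / 0.95 rounds up to 142, close to the stated 140. (Section 4.5 does not state the leakage rates used, so that pair is an assumption.) Both calculations use the full two-sided 0.05, so no alpha is set aside.

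**2. Counting the tests.** From the 13 items in section 6.2, leave out:
- leakage, whose status is disputed
- the inflammatory response, whose markers and time points are not fixed in number
- aspiration pneumonia and gastric volume, which are safety measures
- the cost-effectiveness ratios.

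Eight items remain. Six count once: functional recovery, surgical complications, length of stay, intestinal barrier, additional interventions and faecal composition. ICU counts twice and quality of life four times. Total: 6 + 2 + 4 = 12. The recovery, hospital-use and quality-of-life part is functional recovery, length of stay, two ICU tests and four quality-of-life tests, which makes 8, or 9 with additional interventions.

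**3. Chance of at least one P below 0.05 when nothing differs.** For independent tests the formula is 1 − 0.95^k:
- k = 8: 1 − 0.663 = 33.7%
- k = 9: 1 − 0.630 = 37.0%
- k = 12: 1 − 0.540 = 46.0%.

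For correlated tests, each statistic was simulated as √ρ × G + √(1 − ρ) × E, with G shared across tests and E separate for each (200,000 to 400,000 replicates). A trial was counted if any absolute value exceeded 1.96.

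| Tests (k) | ρ = 0 | 0.3 | 0.5 | 0.7 | 0.8 |
|---|---|---|---|---|---|
| 7 | 30% | 27% | 23% | 18% | 15% |
| 8 | 34% | 30% | 25% | 19% | 16% |
| 9 | 37% | 33% | 27% | 20% | not run |
| 12 | 46% | 40% | 32% | 23% | 19% |

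Counting only results in favour of nutrition, 12 tests give 26% (ρ = 0), 16% (0.5) and 9% (0.8), against 2.5% for one test. The number of tests and ρ are assumptions; the documents give neither.

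**4. Overlap between the two ICU tests.** ICU stay is zero for everyone not admitted, so the two tests nearly coincide. With 140 per group and assumed ICU rates of 3% to 10%, their statistics correlated at 0.998 or more, and the pair rejected in 3.9% to 5.0% of simulated trials. Counting the pair once turns 12 tests into 11 and 8 or 9 into 7 or 8. At ρ = 0.5, 10 tests give 29% and 12 give 32%, so 11 lies between; 7 or 8 give 23% to 25%. In the other direction, testing several scales per questionnaire would raise every figure.

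**The case against.** The strongest reply is that the P<0.05 statement is an ordinary per-test convention, and that the plan nowhere promises familywise control across secondary endpoints. Each secondary test does have about its stated 5% level, so setting a familywise rate against that 5% compares two different quantities. Reading unadjusted secondary results as supportive is also common practice, the primary/secondary split is a basic ranking, and sections 4.5 and 9 already call for risk ratios with 95% confidence intervals. None of the 12 endpoints counted has a power statement.

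Most of this stands. It makes the gap one of labelling and claims; no calculation in the plan is wrong. It does not close the gap, because the written rule overrides the label: any secondary P below 0.05 is significant by the plan's own definition, whatever the ileus result. The label is itself unsettled for leakage. The existing interval statement covers risk ratios, so it does not serve continuous endpoints.

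A reader might infer four stronger things that the documents do not support:
- **That about a third of null trials would give a false recovery, hospital-use or quality-of-life finding.** Those are 8 or 9 tests, or 25% to 27% at a correlation of 0.5. A third needs 8 independent tests, or all 12 at 0.5.
- **That the criterion is the primary endpoint's own rule carried over.** It is worded generally.
- **That the primary test is inflated.** Testing secondary endpoints does not change its level. (The interim look for benefit in section 8.6 is a separate matter.)
- **That secondary results are intended to support adoption of the feed.** No section says so.

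**Conclusion.** The point holds as a gap in the decision rule. One general criterion covers every endpoint, and nothing separates confirmatory from supportive results beyond a label that the documents apply inconsistently. The chance of at least one false significant secondary result when nothing differs is roughly 19% to 46%. This assumes 12 tests, one per item, equally correlated from 0.8 down to 0, and treating the ICU pair as one test lowers it slightly. For the narrower recovery, hospital-use and quality-of-life group it is about 25% to 27%, assuming 8 or 9 tests and a correlation of 0.5. The sample size is not affected. The change is worth making because it is cheap and alters what the trial may claim after a null primary result.

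**What to change.** First reconcile sections 2.1, 4.5 and 12.1(d) with sections 6.1 and 6.2 on whether leakage is primary or secondary; the rule cannot be applied until that is settled. Then replace the significance sentence in sections 4.5 and 9 with text to this effect:

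> The two-tailed P<0.05 decision rule applies to the primary endpoint. All other efficacy endpoints in section 6.2, including the inflammatory markers, are supportive. They are reported as effect estimates with 95% confidence intervals, unadjusted for multiplicity, and no claim of statistical significance is made for them. Safety comparisons are reported unadjusted.

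If a confirmatory claim is wanted on a few secondary endpoints, name them in advance. Test them only after a significant primary result, either in a fixed order at 0.05 or with Holm at 0.05.

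The cost is a few sentences in two sections, with no extra patients, data or alpha penalty on the primary test. The downside is that an isolated P below 0.05 on a secondary endpoint can no longer be reported as a significant effect.

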### **8.5 Data and safety monitoring board**

An independent data and safety monitoring board (DSMB) will evaluate the progress of the trial and will examine safety variables. SAE's need to be reported to the principal investigator within 24 hours, some SAE's will be specified such as: re-intervention, respiratory failure, aspiration pneumonia, myocardial infarction, transfer to the ICU for any reason. Per 10 patients, individualized patient data will be presented to the DSMB. After full explanation of the data presented, the members of the DSMB discuss the consequences of the data presented separately. Besides the assessment of SAE's and AE's a safety analysis will be made after inclusion of 40 patients. In this analysis there is a special focus on gastric

volumes which will be compared as well as incidence of aspiration pneumonia. Adverse events will be listed and discussed with the DSMB. The outcome of the meeting of the DSMB will be discussed with the research group. The outcome will also be sent to the Medical Ethics Committee. All possible adverse events will be reported to the Central Committee on Research involving Human Subjects (Centrale Commissie Mensgebonden Onderzoek (CCMO)) and the IRB using the online module <https://toetsingonline.ccmo.nl>.

The DSMB includes:

1. Prof [name], Emeritus [name]
2. Dr. [name], Gastroenterologist
3. Dr. [name], Intensive Care Medicine
4. Dr. [name], Epidemiologist.

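### Aspiration pneumonia, the named potential risk, is analysed only as a risk ratio tested at P<0.05, which gives a weak basis for a safety statement; a risk difference with a score interval should be prespecified

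*Combined protocol and SAP*

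**What the plan says.** Section 6.2 lists "Aspiration pneumonia" among the secondary endpoints, and section 12.2 identifies it as the potential risk of the intervention. Section 9 then sets the analysis: "Occurrences of the primary and secondary endpoints are compared between the treatment groups". It continues: "Results are presented as risk ratios with corresponding 95% confidence intervals". A two-tailed P below 0.05 "is considered statistically significant". The tests are the unpaired t-test where appropriate, "otherwise the Mann-Whitney U or Chi-square tests", so chi-square is the only one that suits a yes/no event. Section 4.5 repeats the risk-ratio and P<0.05 rule.

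For aspiration pneumonia the text gives no expected rate, risk difference, handling of an empty arm, margin or precision target.

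The size of the trial is set elsewhere, by leakage: "Using a power of 0.8 and a drop-out percentage of 5% a total of 140 patients are needed per group". There is also an early look. Section 4.5 says that "an interim analysis is performed after inclusion of 40 patients in which feasibility and safety of preoperative nutrition are assessed", and section 8.5 puts special focus on gastric "volumes which will be compared as well as incidence of aspiration pneumonia".

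**The concern.** A risk ratio needs control events. For an uncommon harm the control arm may have none, and then the ratio has no finite value. With one or two control events the ratio exists, but its interval can span more than an order of magnitude. The accompanying test has little power unless the harm is common or the increase large.

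Feeding during surgery is described as a new concept. Clinicians will want to know how large an increase in aspiration pneumonia the trial leaves possible. The planned analysis may not give that figure, and P>0.05 does not supply it. A risk difference with a suitable interval does, and it stays defined with an empty arm.

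**Working it through.** **Inputs.** From the documents: 140 per group (section 4.5); two-sided 5% level, risk ratio and chi-square (section 9); early look at 40 patients (sections 4.5 and 8.5), taken as 20 per arm. Not in the documents: the risk of aspiration pneumonia. Control risks of 0.5% to 5% are assumed below.

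**The plan's 140 per group.** Section 4.5 does not say which leakage rates were used. Taking 13% vs 3% from the sham-feeding study, with 80% power and a mean of 0.08:

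- n = [1.96·√(2·0.08·0.92) + 0.842·√(0.13·0.87 + 0.03·0.97)]² / 0.10² = (0.752 + 0.317)² / 0.01 = 114.3, so 115.
- With continuity correction: 133.6, so 134.
- With 5% drop-out: 134/0.95 = 141.1, so 142, close to the stated 140.

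The number is plausible for leakage. It was not chosen for aspiration pneumonia.

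**Empty control arm and power at 140 per arm.** P(no control event) = (1 − p)^140; for example 0.99^140 = 0.245. Power is the exact sum of the two binomial probabilities over all outcomes with uncorrected chi-square P<0.05.

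| Assumed control risk | Control arm empty | Power, risk doubled | Power, risk tripled |
|---|---|---|---|
| 0.5% | 50% | 3% | 8% |
| 1% | 24% | 9% | 20% |
| 2% | 6% | 15% | 39% |
| 3% | 1% | 22% | 57% |
| 5% | 0.1% | 35% | 81% |

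With 133 per arm (140 less 5%), the first four empty-arm figures become 51%, 26%, 7% and 2%.

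**Example 1: 4 fed vs 1 control event.**

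- Risk ratio 4.0; SE of the log ratio = √(1/4 − 1/140 + 1/1 − 1/140) = 1.112; 95% CI 4·exp(±1.96·1.112) = 0.45 to 35.
- Risk difference 2.86 − 0.71 = +2.1 points. Wilson limits are 1.12% to 7.12% (fed) and 0.13% to 3.93% (control).
- Newcombe lower limit = 2.14 − √[(2.86 − 1.12)² + (3.93 − 0.71)²] = −1.5; upper limit = 2.14 + √[(7.12 − 2.86)² + (0.71 − 0.13)²] = +6.4.

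The ratio's interval says little. The difference says that an excess above about 6.4 points is unlikely.

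**Example 2: 4 fed vs 0 control events.**

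- The ratio has no finite value.
- Risk difference +2.9 points; score interval about +0.1 to +7.1, Newcombe −0.3 to +7.1.
- Chi-square = 0.02857² / (0.01429·0.98571·2/140) = 4.06, P = 0.044. Fisher's exact P = 0.122.

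**Would an exact test be better?** With equal risks of 0.5%, 1% and 2%, the chi-square false-positive rate is 0.6%, 2.6% and 4.5%, already within 5%. Fisher's test lowers power from 20% to 8% for 1% vs 3%, and from 50% to 36% for 1% vs 5%.

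**The 40-patient look.** With 0 events in 20 fed patients, the upper limit is 1 − 0.05^(1/20) = 13.9% (one-sided 95%) or 1 − 0.025^(1/20) = 16.8% (two-sided). A true risk of 5% would show no case with probability 0.95^20 = 36%.

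**The case against.** The strongest reply is that patient safety does not depend on this test. Under section 8.5 the DSMB receives individual data per 10 patients, aspiration pneumonia is a specified SAE, and adverse events are listed. Appendix II makes the DSMB responsible for event triggers and stopping guidelines, and provides for suspension if events are too frequent. That stands, and it covers safety during the trial. It does not supply the between-arm estimate that will be reported at the end.

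A second reply is that section 9 names no interval method, and a score interval for the ratio copes with an empty control arm. That is partly right. For 4 vs 0 such an interval has a lower limit of about 1.06 but no finite upper limit, and the upper limit is what a safety statement needs. If only the fed arm is empty, the ratio is zero and is defined, so only an empty control arm is counted above.

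A reader might infer more than the documents support:

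- *Few events are expected, so the ratio will often be undefined.* No rate is given. This holds at control risks of about 1% or below, and fades from 2% upward.
- *Even a tripling would be missed.* From 3% or 5% a tripling is detected with 57% or 81% power.
- *The plan treats P>0.05 as proof of safety.* It nowhere says so. It only states no other criterion for the final comparison.
- *The 40-patient look must yield a risk ratio at P<0.05.* Neither section 4.5 nor section 8.5 requires that.

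**Conclusion.** The point holds as a gap in the analysis plan. The named potential risk has no method suited to sparse events, and the general rule gives weak information about harm. The part that does not depend on assuming very few events is the low power: at most about 35% for a doubling across assumed control risks of 0.5% to 5%. The missing ratio does depend on the rate: about 50%, 24%, 6% and 1% of trials at 0.5%, 1%, 2% and 3%. All these figures assume 140 per arm and rates that the documents do not state. A non-significant result cannot by itself support a safety conclusion. This affects how the final safety result can be read, not the primary endpoint or the DSMB's ongoing oversight.

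**What to change.** In section 9, add for aspiration pneumonia:

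1. Report the count and risk per arm and the risk difference with a score-type 95% confidence interval, beside the risk ratio where it is defined. Name one interval method in advance, since Example 2 shows that the choice can decide whether zero is included. The asymptotic score interval fits the chi-square test there; Newcombe's does not.
2. Base the safety statement on the upper limit of the difference, not on P>0.05.

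Name the endpoint rather than using a trigger such as fewer than five events in an arm. Such a switch depends on the data and would also catch leakage: at the 3% intervention rate in section 4.5, fewer than five events in 140 has a probability of 59%. Keep the chi-square test, for the reason shown in the working.

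Give the DSMB the same counts and intervals at the 40-patient look, with a note that 0 of 20 fed patients leaves a risk of up to about 14% (one-sided) or 17% (two-sided) not excluded.

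The cost is a few sentences, with no extra patients or data. The downside is a less favourable safety statement: even with no event in either arm of 140, the Newcombe interval for the difference runs from −2.7 to +2.7 points.

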### **4.4 Definitions**

Anastomotic leakage is defined as clinical and radiological signs of anastomotic leakage, or confirmed by re-operation or occurrence of an enterocutaneous fistula. Postoperative ileus will be assessed as time to first flatus and defaecation and by measurements of gastrointestinal transit times via ultrasonography (using antrum measurements). Aspiration pneumonia is defined as inflammation in the lungs following aspiration of material (solid or liquid, vomit, saliva).

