### 6.3 Randomisation, blinding and treatment allocation

After obtaining written informed consent patients will be randomly assigned to one of two groups by randomization software (TENALEA Clinical Trial Data Management System). The randomization list was generated by this computerized program using random blocks with maximum block size 6, stratified by operation location (colon or rectum) and operation type (laparoscopic or open). Blinded, study-specific enteral feeding systems are prepared and coded according to this list. A corresponding randomization website will be used that generates the sequential randomization number corresponding to the stratified randomization list upon randomization of a patient. All patients will receive a selfmigrating nasojejunal tube (Flocare Benchmark) one day before surgery. The position of the nasojejunal tube is controlled by abdominal X-ray at the day before surgery. Enriched enteral nutrition (Danone research™) is lead through a programmed Flocare enteral feeding pump. The pump is connected to an opaque branched enteral feeding system (produced by ECM bv, Gemert, the Netherlands) that is connected both to the nasojejunal tube and to a sealed container.

Three hours before surgery the pump is started to administer nutrition in standardized amounts.

Patients are either allocated to the experimental group, in which the blinded branched enteral feeding system leads the enteral nutrition via the nasojenunal tube to the patient. Via this route, the patients in the experimental group will receive the enteral nutrition just before, during and directly after surgery.

In patients allocated to the control group, the blinded branched enteral feeding system leads the enteral nutrition to the container. Consequently, when the feeding pump starts just before surgery, patients in the control group do not receive the nutrition. In both groups, the pump with enteral nutrition is stopped 6 hours after surgery and normal intake is resumed. The used enteral feeding systems are stored by an independent person, to create a checkpoint whether allocation to intervention and control group happened correctly.

The study is blinded for the patient, the surgeon and nursing staff. A protocol explaining the study design and blinding is attached (Appendix A)

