Quality of life is measured via a checklist (EQ-5D-5L and EORTC QLQ C-30) for cancer patients pre- and postoperatively. Long-term outcome parameters such as local recurrence, overall and cancer-specific survival will be registered in a database. Healthcare costs, costs to patients and family are measured at the individual level using data from registration systems of the hospitals and patient questionnaires (including adapted version of the iMTA Medical Consumption Questionnaire (iMCQ) and the iMTA Productivity Cost Questionnaire (iPCQ)).

Preoperatively and on the fourth postoperative day, a total of two fecal samples will be collected. Using the E-Nose, composition of the luminal microbiome will be determined.

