**Postoperatief Beloop**

Epiduraal:  Nee  Ja  
 in datum \_\_\_ / \_\_\_ / 20\_\_\_  
 uit datum \_\_\_ / \_\_\_ / 20\_\_\_

Postop NSAID  Nee  Ja  
 Welke \_\_\_\_\_ start \_\_\_ / \_\_\_ / 20\_\_\_  
 Dosering: \_\_\_\_\_ stop \_\_\_ / \_\_\_ / 20\_\_\_  
 Oraal / iv

Postop Opioid  Nee  Ja  
 1. Welke \_\_\_\_\_ start \_\_\_ / \_\_\_ / 20\_\_\_  
 Dosering: \_\_\_\_\_ stop \_\_\_ / \_\_\_ / 20\_\_\_  
 Oraal / iv / im

2. Welke \_\_\_\_\_ start \_\_\_\_ / \_\_\_\_ / 20 \_\_\_\_  
 Dosering: \_\_\_\_\_ stop \_\_\_\_ / \_\_\_\_ / 20 \_\_\_\_  
 Oraal / iv / im

Postop antibiotica  Nee  Ja  
 Welke \_\_\_\_\_ start \_\_\_\_ / \_\_\_\_ / 20 \_\_\_\_  
 Dosering: \_\_\_\_\_ stop \_\_\_\_ / \_\_\_\_ / 20 \_\_\_\_  
 Oraal / iv

Maagsonde:  Nee  Ja  
 in datum \_\_\_\_ / \_\_\_\_ / 20 \_\_\_\_  
 uit datum \_\_\_\_ / \_\_\_\_ / 20 \_\_\_\_

Orale intake, 24 uur tolerantie: datum \_\_\_\_ / \_\_\_\_ / 20 \_\_\_\_ Tijdstip \_\_\_\_ : \_\_\_\_ uur  
 Eerste flatus datum \_\_\_\_ / \_\_\_\_ / 20 \_\_\_\_ Tijdstip \_\_\_\_ : \_\_\_\_ uur  
 Eerste defaecatie datum \_\_\_\_ / \_\_\_\_ / 20 \_\_\_\_ Tijdstip \_\_\_\_ : \_\_\_\_ uur

POI:  Nee  Ja  
 Interval from surgery until both the following criteria are met:  
 a. Passage of flatus OR stool  
 b. Tolerance of an oral diet  
 These events should occur before day four postoperatively.

Prolonged POI:  Nee  Ja  
 defined if two or more of the following five criteria are met on or after day four postoperatively without prior resolution of "POI" (as described above):  
 Nausea or vomiting  
 Inability to tolerate an oral diet over last 24 h  
 Absence of flatus over last 24 h  
 Abdominal distension  
 Radiologic confirmation

Opname IC:  Nee  Ja  
 in datum \_\_\_\_ / \_\_\_\_ / 20 \_\_\_\_  
 uit datum \_\_\_\_ / \_\_\_\_ / 20 \_\_\_\_  
 reden IC opname: \_\_\_\_\_

Postoperatieve complicaties:  Geen complicaties

Naadlekkage  Nee  Ja, datum vaststellen: \_\_\_\_ / \_\_\_\_ / 20 \_\_\_\_  
 Klinische tekenen AL  
 Radiologische tekenen AL  
 Bevestigd bij reoperatie  
 enterocutane fisteling

Aspiratiepneumonie  Nee  Ja, datum vaststellen: \_\_\_\_ / \_\_\_\_ / 20 \_\_\_\_

Overige postoperatieve complicaties:

_____	Clavien-Dindo graad: _____

Reoperatie:  Nee  Ja, datum \_\_\_ / \_\_\_ / 20\_\_\_

Reden: \_\_\_\_\_

Overplaatsing ander ziekenhuis:  Nee  Ja, datum \_\_\_ / \_\_\_ / 20\_\_\_

Functioneel hersteld: datum \_\_\_ / \_\_\_ / 20\_\_\_

(ADL zelfstandig, eten, drinken etc)

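### Section 9 names only unadjusted two-sample tests and a risk ratio, so the collected baseline quality-of-life scores and the randomisation strata go unused; the cost is precision, mainly for quality of life

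*Combined protocol and SAP*

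**What the plan says.** The secondary endpoints in section 6.2 include "Quality of life (EQ-5D-5L and EORTC-QLQ-C30 at baseline, after 3 and 6 months". Section 6.4 adds only: "Quality of life is measured via a checklist (EQ-5D-5L and EORTC QLQ C-30) for cancer patients pre- and postoperatively". Neither section says how the scores are analysed.

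Section 6.3, repeated in section 11.1, states that randomisation is "stratified by operation location (colon or rectum) and operation type (laparoscopic or open", which gives four strata.

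Section 9 is the whole analysis plan. Its tests are "an unpaired T-test will be performed when appropriate, otherwise the Mann-Whitney U or Chi-square tests", and its only effect measure is the risk ratio: "Results are presented as risk ratios with corresponding 95% confidence intervals". It mentions no covariate, baseline value, change score, stratified test or repeated-measures model, and no main QoL scale or time point. Section 4.5 repeats the general wording and adds nothing on adjustment.

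**The concern.** Two pieces of information that the trial will hold are left out of the analysis.

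- **Baseline QoL.** Section 9 does not say whether the baseline score is used. An unpaired t-test could be run on follow-up scores or on change from baseline, and the two estimates differ by exactly the chance baseline difference between the arms. Either is valid if fixed beforehand, and both are less precise than an analysis with baseline as a covariate. A risk ratio cannot describe a difference in scores.
- **The strata.** Stratified blocks balance the arms on location and operation type. An unadjusted standard error still counts the variation between strata as noise, so it is somewhat too large when the strata predict outcome.

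At stake are the precision of a declared secondary endpoint, some freedom in choosing its analysis, and a small amount of efficiency for POI.

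**Working it through.** **The plan's own figure.** POI at 47% versus 27% (section 4.5: "postoperative ileus was reduced from 47% in the controls to 27% in the intervention group"), two-sided 0.05, power 0.80, pooled variance, mean risk 0.37:

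n = [1.96 × √(2 × 0.37 × 0.63) + 0.8416 × √(0.47 × 0.53 + 0.27 × 0.73)]² / 0.20² = (1.338 + 0.562)² / 0.04 ≈ 90.3, so 91 per group, as stated. The planned size is 140 per group with 5% drop-out: 140 × 0.95 = 133.

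**QoL.** Assumptions, none given in the documents: 133 complete scores per arm, equal SDs, normal-theory tests, baseline to follow-up correlation ρ = 0.3 / 0.5 / 0.7, and a true difference of 0.3 SD for power.

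The standard error (SE) of a difference in follow-up scores is √(2/133) = 0.123 SD, so the chance baseline difference lies within ±1.96 × 0.123 = ±0.24 SD in 95% of trials. In units of the follow-up variance, the variances are 1 (follow-up), 2(1 − ρ) (change) and 1 − ρ² (ANCOVA). The interval reductions from ANCOVA are therefore 1 − √(1 − ρ²) against follow-up and 1 − √((1 + ρ)/2) against change.

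| ρ | ANCOVA vs follow-up | ANCOVA vs change | Power: follow-up | Power: change | Power: ANCOVA |
|---|---|---|---|---|---|
| 0.3 | 5% narrower | 19% narrower | 69% | 54% | 73% |
| 0.5 | 13% narrower | 13% narrower | 69% | 69% | 81% |
| 0.7 | 29% narrower | 8% narrower | 69% | 88% | 93% |

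Example at ρ = 0.5: 0.3 / (0.123 × √0.75) = 2.82, and Φ(2.82 − 1.96) = 0.81. The percentage reductions do not depend on the number of complete scores; the power figures do.

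*Choice between follow-up and change scores.* Their test statistics have correlation √((1 − ρ)/2) = 0.59 / 0.50 / 0.39. With no effect, the bivariate normal gives a chance of 8.78 / 9.07 / 9.35% that at least one is significant at 5%.

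**POI as yes/no.** Simulation with 400,000 trials per scenario and equal allocation within four strata. The treatment odds ratio is constant and set to give 47% versus 27% overall. Assumed stratum sizes are 59/27/27/20 per arm (133) or 62/28/28/22 (140). The assumed odds ratio (OR) per stratification factor is 1 / 1.5 / 2 / 3; for the last three the control risks are about 40/50/50/60%, 35/52/52/68% and 29/55/55/79%.

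| OR per factor | Chi-square power (133) | Cochran-Mantel-Haenszel (CMH) power (133) | Chi-square type I error (140) |
|---|---|---|---|
| 1 | 92.6% | 92.6% | about 4.8% |
| 1.5 | 92.9% | 93.0% | about 4.5% |
| 2 | 93.3% | 93.9% | about 4.2% |
| 3 | 93.9% | 95.4% | about 3.4% |

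The gain is 0 / 0.1 / 0.6 / 1.5 power points. The Mantel-Haenszel risk-ratio interval is 0 / 0.7 / 2.3 / 5.6% narrower.

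**POI as a time.** If the two factors explain an assumed 2 / 5 / 10% of the variance, the interval is 1 − √(1 − R²) = 1.0 / 2.5 / 5.1% narrower.

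**Leakage.** At 13% versus 3.25% (a 75% reduction, 13 × 0.25), the interval is 0 to 1.4% narrower.

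**The case against.** The strongest reply is that nothing here is invalid. Randomised arms compared by unadjusted tests give unbiased results, and POI power stays above the planned 80% either way. That stands. A reader might infer from the stratified design that the plain chi-square test breaks the 5% level. The working shows the opposite: its error falls as the strata become prognostic.

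A reader might also infer that this conservatism appears only with strongly prognostic strata, because at 133 per arm the simulated error with non-prognostic strata is above 5%. That is an effect of discreteness at one sample size. The exact unstratified error at a 47% risk is 5.7% at 133 per arm, 5.0% at 134, 4.6% at 135 and 4.8% at 140. At 140 the test is already mildly conservative at an odds ratio of 2.

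Secondly, section 9 never mentions change scores, and its plain reading is a comparison of the arms at each time point. This also stands. The 9% is therefore an upper bound, reached only if both analyses are run and the significant one is always reported; the documents give no sign that this is intended.

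Thirdly, the QoL figures are conditional. Section 9 sends non-normal scores to Mann-Whitney, which the figures do not cover. The 133 borrows the drop-out rate of the leakage calculation. Section 6.4 ties the questionnaires to cancer patients, while section 4.2 does not require cancer, so fewer scores may be available. At a correlation of 0.3 the gain over follow-up scores is only about 5% in interval width. These points limit the size of the gain but do not remove it.

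**Conclusion.** The point holds as one of precision and pre-specification, mainly for a secondary endpoint. For QoL, under the stated assumptions, ANCOVA narrows the interval by about 5 to 29% against follow-up scores and 8 to 19% against change scores. At 0.3 SD it raises power from 69% with follow-up scores to 73 / 81 / 93%. An open choice between follow-up and change scores could cost at most about 9% type I error per scale and time point.

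For yes/no POI, using the strata is an efficiency gain of about 0 to 1.5 power points. It does not repair a faulty test, and the primary conclusion is not threatened. Leakage is practically unaffected.

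The correlations, the 0.3 SD, the number of complete scores, and the stratum sizes, risks and variance shares are assumptions; the documents give none of them.

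How POI is defined is a separate issue. It appears as a proportion in section 4.5, as times in section 4.4 ("Postoperative ileus will be assessed as time to first flatus and defaecation"), and in the case report form as a yes/no box worded as an interval ("Interval from surgery until both the following criteria are met"). The small effect found here concerns only the unused strata and says nothing about that question.

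**What to change.** In section 9:

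- **QoL.** Specify one analysis: ANCOVA at 3 months and at 6 months for each EQ-5D-5L and QLQ-C30 score, with the baseline score and the two stratification factors as covariates, reported as an adjusted mean difference with 95% CI. Name the main scale and the main time point. Give the unadjusted comparison of follow-up scores as the single supporting analysis. Offering ANCOVA or a mixed model as alternatives, or an unspecified unadjusted result, would leave open the choice that this point is about.
- **POI.** If analysed as yes/no, report a Mantel-Haenszel risk ratio with 95% CI and a CMH test over the four strata. If analysed as a time, include the same two factors. Use the strata as entered at randomisation, not the procedure recorded afterwards, since the operation page of the case report form also records conversion.
- **Leakage.** No change is needed on this point.

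The cost is a few sentences and slightly more analysis work, with no new data and no change in sample size. For yes/no POI the effect measure stays a risk ratio, and if the strata turn out not to be prognostic the power cost is under 0.1 points.
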